10.4.1 Inclusion Criteria

To be confirmed at Screening

1. Healthy male and female participants 18 to 45 years of age, inclusive.
2. Female participant of childbearing potential willing to use 2 effective methods of contraception, i.e., established method of contraception + condom, if applicable (unless of non-childbearing potential or where abstaining from sexual intercourse is in line with the preferred and usual lifestyle of the participant) from the first dose until 2 months after the last dose of IMP.
3. Female participant of non-childbearing potential. *For the purposes of this study, this is defined as the participant being amenorrhoeic for at least 12 consecutive months or at least 4 months post-surgical sterilisation (including bilateral fallopian tube ligation or bilateral oophorectomy with or without hysterectomy).*
4. Female participant of childbearing potential or non-childbearing potential with a negative pregnancy test at Screening.
5. Female participant of post-menopausal status confirmed by demonstrating at Screening that the serum level of the follicle stimulating hormone (FSH) falls within the respective pathology reference range. In the event a participant's menopausal

status has been clearly established (for example, the participant indicates she has been amenorrhoeic for 10 years, confirmed by medical history, etc), but serum FSH levels are not consistent with a postmenopausal status, determination of the participant's eligibility to be included in the study will be at the Investigator's discretion following consultation with the Sponsor.

6. Male participant willing to use an effective method of contraception or 2 effective methods of contraception, i.e., established method of contraception + condom, if applicable (unless anatomically sterile or where abstaining from sexual intercourse is in line with the preferred and usual lifestyle of the participant) from first dose until a stool sample tested for presence of the vaccine strains is negative .
7. Participant with a BMI of ≥ 19 or $\leq 34 \text{ kg/m}^2$ ($\text{BMI} = \text{body weight (kg)} / [\text{height (m)}]^2$).
8. No clinically significant history of liver or active gall bladder disease.
9. No clinically significant history of ongoing gastro-intestinal disease or abnormality.
10. No clinically significant history of previous allergy / sensitivity to ZH9/ZH9PA or sodium bicarbonate.
11. No clinically significant history of anaphylactic shock following vaccination.
12. No clinically significant history of hypersensitivity (e.g., hives/rash/swollen lips/difficulty with breathing) to azithromycin, ampicillin, trimethoprim-sulfamethoxazole or ciprofloxacin.
13. No clinically significant abnormal laboratory test results (in the opinion of the investigator) for serum biochemistry, haematology and/or urine analyses within 28 days before receiving the first dose administration of the IMP.
14. Participant with a negative urinary DOA screen (including alcohol and cotinine) test results, determined within 28 days before the first dose administration of the IMP unless there is a documented medical explanation for the positive result other than drugs of abuse (e.g., the participant has been prescribed opioids for pain). (N.B.: A positive test result may be repeated at the Investigator's discretion).
15. Participant with negative HIV, HBsAg and HCV Ab test results at Screening.
16. No clinically significant abnormalities in 12-lead electrocardiogram (ECG) or vital signs determined within 28 days before first dose of IMP.
17. Participant must be available to complete the study (including all follow up visits).
18. Participant must be willing to consent to have data entered into TOPS.
19. Participant must provide written informed consent to participate in the study.

To be re-confirmed on Day 0 / prior to each dosing visit

1. Participant continues to meet all screening inclusion criteria.
2. Participant with a negative urinary drugs of abuse screen (including alcohol and cotinine) prior to dosing unless there is a documented medical explanation for the

positive result other than drugs of abuse (e.g., the participant has been prescribed opioids for pain). (N.B.: A positive test result may be repeated at the Investigator's discretion).

3. Female participant of childbearing potential or non-childbearing potential with a negative pregnancy test on admission.

10.4.2 Exclusion Criteria

To be confirmed at Screening

1. Participant with any clinically significant medical (cardiovascular disease, pulmonary, hepatic, gallbladder or biliary tract, renal, haematological, gastrointestinal, endocrine, immunologic, dermatological, neurological, autoimmune disease or current infection) or psychiatric condition (see also exclusion criterion number 21) that, in the opinion of the Investigator, precludes participation in the study. This will include any clinically significant abnormal serum biochemistry results and/or haematological results and/or urine analytical results.
2. Participant with a history of heart disease or of rheumatic fever.
3. Participant with a significant acute febrile illness (including fever of 38.0°C or greater within 14 days) of each dose of IMP (Days 0, 21 and 42).
4. Participant who has chronic diseases: Chronic diseases will include all autoimmune and immunocompromising conditions and any other chronic condition, which at the judgment of the Investigator, may put the participant at higher risk of side effects from the study vaccine. Conditions in the latter category might include unexplained anaemia, hepato-biliary disease, uncontrolled hypertension, participant with prosthetic joints or heart valves, etc.
5. Participant with sickle cell anaemia.
6. Participant who has undertaken a course of antibiotics/antibacterials within 28 days prior to each dose of IMP (Days 0, 21 and 42).
7. Use of prescription or non-prescription drugs within 28 days or 5 half-lives (whichever is longer) prior to receiving the first dose of IMP, unless in the opinion of the Investigator and Sponsor's Responsible Physician the medication will not interfere with the study procedures or compromise participant safety.
8. Participant who uses antacids, proton pump inhibitors or H₂ blockers on a regular basis or has consumed proton pump inhibitors or H₂ blockers within 24 hours prior to each dose of IMP.
9. Participant who has received investigational or licensed vaccines in the 28 days prior to dosing or anticipates receiving a vaccine other than study medication up to Day 84 of the study.
10. Participant with symptoms consistent with Typhoid fever concurrent with travel to countries where typhoid infection is endemic (most of the developing world) within 2 years prior to first dose of IMP.

11. Vaccination against Typhoid within 3 years prior to first dose of IMP.
12. Ingestion of Typhoid bacteria in a challenge study within 3 years prior to dosing.
13. Participant who works as a commercial food handler.
14. Participant who is a health care worker in direct contact with patients.
15. Participant who is a childcare worker.
16. Participant who has household contact with immuno-compromised individuals, pregnant women, children < 2 years of age or individuals > 70 years of age.
17. Participant who has person(s) living with him/her who, in the opinion of the Investigator, may be at risk of disease if exposed to the vaccine strain.
18. Participant with a known impairment of immune function or receiving (or have received in the 6 months prior to study entry) cytotoxic drugs or immunosuppressive therapy (including systemic corticosteroids).
19. Participant who is current smoker (cigarettes, tobacco and/or e-cigarettes) or have stopped smoking in the last 3 months prior to Screening.
20. A clinically significant history of drug or alcohol abuse [defined as the consumption of more than 14 units of alcohol a week] within the past two years prior to Screening.
21. Inability to communicate well with the Investigators (i.e., language problem, poor mental development or impaired cerebral function).
22. Participation in a NCE clinical study within the previous 3 months or a marketed drug clinical study within the 30 days before the first dose of IMP. (*Washout period between studies is defined as the period of time elapsed between receiving the last dose of the previous study and receiving the first dose of the next study*).
23. Donation of 450 mL or more blood within the 3 months before the first dose of IMP.
24. Participant who, in the opinion of the Investigator, is unsuitable for participation in the study.

To be re-confirmed at Day 0 / prior to each dosing visit

1. Development of any exclusion criteria since the Screening visit.
2. Use of prescription or non-prescription drugs since Screening, unless in the opinion of the Investigator and Sponsor's Responsible Physician, the medication will not interfere with the study procedures or compromise participant safety.
3. Participation in a clinical study since Screening.
4. Donation of 450 mL or more blood since Screening.

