10.6.7 Selection of Doses in the Study

ZH9 is a live attenuated, oral vaccine, against typhoid fever. It was previously identified as MICRO-TY. ZH9 and consists of the vaccine strain, S. Typhi (Ty2 aroC⁻ ssaV⁻) ZH9.

Individual participant treatments will be dispensed by the pharmacist or designee and labelled in accordance with Annex 13 of “The Rules Governing Medical Products in European Community, volume 4 Good Manufacturing Practice for Medicinal Products”^[4].

The following dosing strategy will be employed:

Cohort	Dose schedule	Dose level
1	Day 0, 21, 42	1x10 ⁹ CFU ZH9PA or placebo
2	Day 0, 21, 42	1x10 ¹⁰ CFU ZH9PA or placebo
3	Day 0, 21, 42	1x10 ¹⁰ CFU ZH9PA and 1x10 ¹⁰ CFU ZH9 or placebo

The dose levels chosen are based on the previous clinical experience with ZH9. These studies have determined that a dose of 1×10^{10} CFU is well tolerated and induces immune responses to LPS 0:9. ZH9PA is derived from ZH9, being modified to carry heterologous antigens. Other potential products, derived from ZH9, have been used to deliver heterologous antigens in clinical trials i.e. ETEC LT antigen and Hepatitis B core antigen, at doses of 1×10^9 CFU and 1×10^{10} CFU respectively. Based on these data it is considered appropriate that the starting dose for ZH9PA is 1×10^9 CFU. To date, ZH9 has been administered at a maximum dose of 1.7×10^{10} CFU with no significant adverse effects; therefore, administering a maximum bacterial load of 2×10^{10} CFU, of ZH9PA with ZH9 is considered appropriate.

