10.7.3 Pharmacodynamic Assessments

The following PD blood samples will be collected at the time-points specified in Table 10.7.1.

- Serum Ig Responses
- PBMC for ALS assay

Detailed sample collection and processing instructions will be documented in the SHM.

The IgG and IgA responses to four antigens (LPS O:9, LPS O:2; H:d, H:a) will be determined by a validated enzyme-linked immunosorbent assay (ELISA) end point titre method.

PBMC will be cultured for 72 hours (+/- 3 hours) and the concentration of IgA in the supernatant specific for the same four antigens will be determined by a validated ELISA end point titre method.

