10.9.1.1 Study Variables/Endpoints

Primary Endpoint

- Local and systemic reactogenicity up to Day 84 as assessed by adverse events, laboratory safety tests (biochemistry, haematology, urinalysis), vital signs and physical examination.

Secondary Endpoints

- Local and systemic reactogenicity; from Day 85 to Day 224 as assessed by adverse events, laboratory safety tests (biochemistry, haematology, urinalysis) if undertaken for cause; vital signs if undertaken for cause; physical exam if undertaken for cause.
- Concentrations of specific serum IgA and IgG antibodies to LPS O:2 and O:9, flagellin H:a and H:d.
- Fold increase in specific serum IgA and IgG antibody concentrations, in individual participants, against the antigens LPS O:2 and O:9, flagellin H:a and H:d.
- Concentrations of specific mucosal IgA antibodies in lymphocyte supernatant (ALS) assays, in individual participants, against antigens LPS O:2 and O:9, flagellin H:a and H:d.
- Seroconversion rate (proportion of participants with 4-fold increase above baseline at any time post vaccination) against each of the above antigens.
- Fold increase in specific mucosal IgA antibodies in lymphocyte supernatant (ALS) assays, in individual participants, against the antigens LPS O:2 and O:9, flagellin H:a and H:d.

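### The recent-exposure exclusions name typhoid vaccination and challenge but no Paratyphi A equivalent, although O:2 and H:a are two of the four endpoint antigens and the only vaccine antigens in Cohorts 1 and 2

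*Combined protocol and SAP*

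**What the plan says.** Three exclusions in section 10.4.2 deal with earlier exposure to the organism:

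- Exclusion 10, with a 2-year look-back: "Participant with symptoms consistent with Typhoid fever concurrent with travel to countries where typhoid infection is endemic".
- Exclusion 11: "Vaccination against Typhoid within 3 years prior to first dose of IMP".
- Exclusion 12: "Ingestion of Typhoid bacteria in a challenge study within 3 years prior to dosing".

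Two general washouts also apply. Exclusion 9 covers any vaccine: "Participant who has received investigational or licensed vaccines in the 28 days prior to dosing". Exclusion 22 covers other trials: "Participation in a NCE clinical study within the previous 3 months", or 30 days for a marketed-drug study. Exclusion 24 leaves general unsuitability to the Investigator.

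Section 10.1 assigns O:9 and H:d to typhoid and O:2 and H:a to Paratyphi A, and says that ZH9PA carries the second pair in place of the first. Antibody to all four is measured (section 10.7.3). Section 10.9.1.1 lists as a secondary endpoint the "Seroconversion rate (proportion of participants with 4-fold increase above baseline at any time post vaccination) against each of the above antigens".

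Section 10.6.7 describes ZH9 as a typhoid vaccine. It adds that "Other potential products, derived from ZH9, have been used to deliver heterologous antigens in clinical trials", naming an ETEC LT and a hepatitis B core construct.

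**The concern.** The protocol treats typhoid vaccination or challenge within three years as a reason to keep someone out. No such window is stated for the organism whose antigens the first-in-human component carries. Those antigens, O:2 and H:a, are in the active vaccine of every cohort; O:9 and H:d are added only in Cohort 3.

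The responder definition is a 4-fold rise over the participant's own baseline. Someone already primed may start high and fall short of 4-fold, or may show a recall response larger than a naive person would. In either case the fold rise describes the vaccine in naive adults less well, and in arms this small one such person is visible in the result.

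**Working it through.** **Coverage, exposure by exposure**

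| Earlier exposure | Criterion that catches it | Window |
|---|---|---|
| Typhoid vaccine, including ZH9 | Exclusion 11 | 3 years |
| Typhoid challenge | Exclusion 12 | 3 years |
| Typhoid-like illness with endemic travel (either serovar, plausibly) | Exclusion 10 | 2 years |
| Paratyphi A vaccine | Exclusion 9 (22 if given in a trial) | 28 days (3 months if it counts as an NCE study) |
| Paratyphi A challenge | Exclusion 22, if it counts as an NCE study | 3 months |
| ZH9-derived ETEC LT or hepatitis B core product | Exclusions 9 and 22; 11 only on a generous reading | 28 days or 3 months |

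A Paratyphi A challenge or vaccine 12 months before Day 0 therefore breaches none of the listed windows. Only Investigator discretion remains.

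**Later safeguards.** Serum for immunoglobulin is first drawn on Day 0 (Table 10.7.2), and no titre limit applies to entry. The Per Protocol Set (section 10.9.1.2) removes vomiting or diarrhoea, interfering medication and major deviations. A primed volunteer who met all criteria is not a deviation, so stays in. Section 10.9.1.3.4 plans an ANOVA/ANCOVA but names no baseline covariate.

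**Weight of one participant.** The plan gives no power figure to reproduce; section 10.9.2 says that the sample size has no formal basis. Section 10.1 gives active arms of 6, 12 and 12 and placebo arms of 3, 6 and 6.

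- Active arm of 6: 1/6 = 16.7 percentage points.
- Active arm of 12: 1/12 = 8.3 percentage points.

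**Effect on the planned Fisher test.** No alpha is stated, so two-sided 0.05 is assumed, with no placebo responders. The plan does not say whether placebo is pooled across cohorts (3 + 6 + 6 = 15), so both cases are shown.

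| Active vs placebo | Fewest responders for p ≤ 0.05 | One fewer |
|---|---|---|
| 12 vs 6 | 7/12, p = 0.038 | 6/12, p = 0.054 |
| 6 vs 3 | 5/6, p = 0.048 | 4/6, p = 0.167 |
| 12 vs 15 | 4/12, p = 0.028 | 3/12, p = 0.075 |
| 6 vs 15 | 3/6, p = 0.015 | 2/6, p = 0.071 |

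Check of the first row. For 7/12 vs 0/6, the observed table has weight C(12,7) = 792 out of C(18,7) = 31,824. The less likely tables add 396 + 12, so p = 1,200/31,824 = 0.038. For 6/12 vs 0/6, p = (924 + 72 + 1)/18,564 = 0.054.

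**Chance that at least one primed person enters.** The prevalence q of priming is not in the documents, so a range is assumed. The chance is 1 − (1 − q)^n.

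| q | n = 6 | n = 12 | All 45 |
|---|---|---|---|
| 1% | 5.9% | 11.4% | 36% |
| 2% | 11.4% | 21.5% | 60% |
| 5% | 26.5% | 46.0% | 90% |

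**Illustrative loss of power (assumed rates).** Suppose that naive vaccinees seroconvert with probability 0.7, placebo never does, and k primed vaccinees miss the 4-fold rise. For 12 vs 6 the power is P(Binomial(12 − k, 0.7) ≥ 7): 88% for k = 0, 79% for k = 1 and 65% for k = 2. For 12 vs pooled 15 it hardly moves: 99.8%, 99.6% and 98.9%. A strong recall response would push the other way.

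**The case against.** Several arguments against the point are sound, and they limit it.

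- **Paratyphoid illness.** A reader might infer that paratyphoid illness is wholly uncovered. The documents do not support that. Exclusion 10 works on symptoms, not serovar, and the Introduction (section 8) uses enteric fever and typhoid as joint names for disease from both. Recent symptomatic paratyphoid after travel is plausibly excluded. The same usage makes exclusions 11 and 12 ambiguous at best, which is itself a reason to state the serovars.
- **ZH9 and its derivatives.** A reader might infer that earlier recipients of ZH9 itself can enter freely, or that ZH9-derived products prime for O:2 and H:a. Neither follows. ZH9 is a typhoid vaccine, so exclusion 11 bars it for three years. The documents ascribe O:2 and H:a only to ZH9PA, which had not been given to humans. The derived constructs bear on O:9 and H:d, so mainly on the 12 active participants of Cohort 3; the 1-in-6 figure does not apply to them. No dates are given for those trials.
- **Role of the Typhi antigens.** They are not a comparator that the criteria favour. They are vaccine antigens of the combination in Cohort 3.
- **Bias.** Randomisation within cohorts and fold rises over own baseline limit systematic bias. A boost after dosing is still caused by the vaccine, even if priming alters its size.
- **Frequency.** The documents mention no Paratyphi A challenge study and no Paratyphi A vaccine other than ZH9PA, so nothing in them shows that any volunteer has had such an exposure. This stands: the likely number is small and cannot be estimated.

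What survives is the uneven wording of the exclusions and the lack of any planned handling of baseline titre.

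**Conclusion.** The gap is real but narrow. Vaccination and challenge with Paratyphi A fall only under the 28-day and 3-month washouts and Investigator discretion, while their typhoid counterparts carry three years. ZH9-derived constructs are a second, smaller gap, mainly for Cohort 3.

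The consequence is possible chance imbalance and distorted fold rises on secondary endpoints, in either direction. The primary safety endpoint is not touched. A reader might go further and infer that the seroconversion results would reflect earlier exposure and not the vaccine. That is not supported, given the placebo groups and the Day 0 baselines.

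The firm figures are 16.7 points per participant in the active arm of 6 and 8.3 points in an arm of 12. That one participant can move a Fisher test across 0.05 rests on the assumed two-sided level and no placebo responders. The entry probabilities and power figures rest on assumed rates and show range only. This is a cheap improvement, not a flaw that threatens the trial.

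**What to change.** 1. Reword exclusions 10 to 12 to read *typhoid or paratyphoid (S. Typhi or S. Paratyphi A)*, keeping the existing 2- and 3-year windows.
2. Extend exclusion 11 to any ZH9-derived investigational product within the same 3 years.
3. Exclusions cannot catch older or asymptomatic priming. In section 10.9.1.3.4, or in the SAP that section 10.9.1 says will be written before database lock, name Day 0 log-titre as the ANCOVA covariate for between-group comparisons. Add a sensitivity summary of fold rise and seroconversion by baseline titre.

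The cost is the rewording of three criteria with matching screening questions, probably a few volunteers lost at screening, and a little more analysis. Day 0 sera are already collected, so no further sampling is needed.

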10.5 Additional Advice and Restrictions for Study Population

10.5.1 Contraception

To prevent pregnancy, female participants of childbearing potential and male participants and their female partner(s) must use 2 reliable forms of contraception, i.e.,

- Condom + Established use of oral, injected or implanted hormonal contraceptive.
- Condom + Intrauterine device.
- Condom + Diaphragm with spermicide.
- True abstinence, when this is in line with the preferred and usual lifestyle of the participant. *[Periodic abstinence (e.g., calendar, ovulation, symptothermal, post-ovulation methods) and withdrawal are not acceptable methods of contraception].*

To prevent exposure of any partner (male or female) during non-vaginal intercourse to the semen from a male participant who has been exposed to the IMP, the following contraception must be used:

- Condom.

The chosen contraception method(s) must be followed from receiving the first dose of IMP until a stool sample tested for presence of the vaccine strains is negative for male participants and at least 2 months after receiving the last dose of IMP for female participants.

Male participants must not have unprotected sexual intercourse with a female who is pregnant or breastfeeding during the study.

10.5.2 Sperm Donation

Male participants must not donate sperm from receiving the first dose of IMP until a stool sample tested for presence of the vaccine strains is negative.

10.5.3 Diet and Fluid Restrictions

10.5.3.1 Meal Times/Fasts

Participants will fast for 90 mins prior to dose administration and 90 mins following dose administration. Water is permitted.

10.5.3.2 Fluid Intake

Water is allowed *ad libitum*.

10.5.3.3 Alcohol Intake

The consumption of alcohol will be limited to a maximum of 2 units per day from 7 days prior to the first dose of IMP. Alcohol will be avoided completely for a period of not less than 2 days prior to screening and each of the 3 doses of IMP. Any deviation outside this alcohol intake restriction will be assessed on a case-by-case basis at Investigator's discretion (provided the participant's alcohol intake will not impact in the safety aspects and objectives of the study and the participant has a negative alcohol screen prior to dosing).

10.5.3.4 Caffeine

Food or drink containing caffeine, including coffee, tea, cola, energy drinks or chocolates will be avoided completely whilst the participants are in attendance at the Clinical Unit (during each dosing period).

